Appendix 2. Drug interactions of TDF/FTC

Drugs not allowed in the trial.

Analgesics
Chronic use (two or more weeks) of any of the following: Celecoxib, Diclofenac, Ibuprofen Methadone Naproxen Nimesulide Piroxicam
Antiarrhythmics
Amiodarone Quinidine
Antibiotics

Amikacin
Cefalexin
Clarithromycin
Gentamicin
Piperacillin/ Tazobactam
Rifampicin
Sulfadiazine
Vancomycin

Contraceptives

Ethinyl estradiol and norgestimate

Anticonvulsants

Topiramate

Antidepressants

Lithium

Antidiabetics

Canagliflozin

Empagliflozin

Antifungal

Amphotericin B

Fluconazole

Itraconazole

Flucytosine

Ketoconazole

Antiretrovirals

Dolutegravir/Lamivudine

Abacavir

Didanosine

Lamivudine

Atazanavir/cobicistat

Atazanavir/ritonavir

Darunavir/ritonavir

Darunavir/cobicistat

Indinavir

Antivirals

Acyclovir

Ganciclovir

Ledipasvir/Sofosbuvir

Sofosbuvir/Velpatasvir

Calcium channel blockers

Verapamil

Antihypertensives / Heart failure

Furosemide

Hydralazine

Sacubitril

Immunomodulators

Interferon

Hydroxyurea

Immunosuppressors

Ciclosporin Mycophenolate Sirolimus Tacrolimus
Others
Acetazolamide Orlistat Probenecid Pyridostigmine Sevelamer Zoledronic Acid

Low interaction drugs allowed in the trial:

References

- HIV Drug interactions. University of Liverpool.
https://www.hiv-druginteractions.org/view_all_interactions/445855
- Ficha técnica TDF/FTC TRUVADA Gilead Sciences Ireland UC
https://www.ema.europa.eu/en/documents/product-information/truvada-epar-product-information_es.pdf

Appendix 3. Variables

Inclusion-exclusion criteria

Variable	Variable type	Conceptual definition	Operative definition
Informed consent signature date	Quantitative	Informed consent signature date	Day/Month/Year
Age	Qualitative/dichotomous	Age 18 to 70 years according to legal ID	0- No 1- Yes
Profession	Qualitative/nominal	Profession	1- Physician 2- Nurse 3- Nursing assistant 4- Respiratory therapist
Caring for COVID-19 patients	Qualitative/dichotomous	Subject has direct contact with confirmed or suspected COVID-19 patients	0- No 1- Yes
Serology IgG for SARS-CoV-2	Qualitative/dichotomous	Result of serology IgG test for COVID-19 before randomization and administration of drug/placebo	0- Negative 1- Positive
Baseline RT-PCR for SARS-CoV-2	Qualitative/dichotomous	Result of RT-PCR for SARS-CoV-2 of nasopharyngeal swab before randomization and administration of drug/placebo	0- Negative 1- Positive
Exclusion criteria			
COVID-19 related symptoms	Qualitative/dichotomous	Presence of two or more of the following at initial screening: - Body temperature ≥ 38 °C - Acute cough (onset less than 10 days) - Shortness of breath - Sore throat - Malaise. - Acute diarrhea	0- No 1- Yes

History of COVID-19	Qualitative/dichotomous	History of serology or rtPCR confirmed COVID-19	0- No 1- Yes
Cohabitation with people with COVID-19 infection or COVID-19 symptoms	Qualitative/dichotomous	Cohabitation with people with COVID-19 infection or COVID-19 symptoms	0- No 1- Yes
Treatment during last month with medications that have significant interactions with TDF/FTC	Qualitative/dichotomous	Treatment during last month with medications that have significant interactions with TDF/FTC (see Appendix 2)	0- No 1- Yes
HIV infection	Qualitative/dichotomous	Confirmed HIV infection	0- No 1- Yes
B hepatitis immunity	Qualitative/dichotomous	Volunteer with anti-HBsAg less than 10 UI/ml	0- No 1- Yes
Hepatitis B infection	Qualitative/dichotomous	History of hepatitis B virus infection	0- No 1- Yes
Recent use of TDF/FTC	Qualitative/dichotomous	Use of TDF/FTC within the last month for any other indication	0- No 1- Yes
Hypophosphatemia	Qualitative/dichotomous	Phosphorus serum concentration less than lower reference laboratory value	0- No 1- Yes
Liver dysfunction	Qualitative/dichotomous	Liver dysfunction as defined by ALT or AST levels \geq 2 times upper limit of normal (x ULN) (66)	0- No 1- Yes
Hematologic dysfunction	Qualitative/dichotomous	Hemoglobin concentration less than 11 mg/dl or neutrophil count less than 1000 cel/mm ³	0- No 1- Yes
Chronic kidney disease	Qualitative/dichotomous	eGFR \leq 60 mL/min/1.73 m ² , calculated by CKD-EPI formula with baseline creatinine or past history of chronic kidney disease as disclosed by volunteer	0- No 1- Yes
Hypersensitivity to TDF/FTC	Qualitative/dichotomous	History of hypersensitivity to TDF/FTC	0- No 1- Yes
Metabolic bone disease	Qualitative/dichotomous	History of osteopenia, osteoporosis or pathologic fractures	0- No 1- Yes
Pregnancy, breastfeeding or plans to seek pregnancy during the study	Qualitative/dichotomous	Pregnancy, breastfeeding or plans to seek pregnancy during the foreseen duration of participation in the study	0- No 1- Yes 2- Not applicable
Pregnancy test	Qualitative/dichotomous	Result of quantitative serum Beta-HCG above the limit of detection of laboratory for non-pregnant women	0- No 1- Yes 2- Not applicable
Participation in another study	Qualitative/dichotomous	Participation in any other study of prevention of COVID-19	0- No 1- Yes
Withdrawal criteria			
Kidney dysfunction	Qualitative/dichotomous	Any grade 2 kidney function adverse event during the study	0- No 1- Yes
Related Serious adverse event	Qualitative/dichotomous	Any serious adverse event deemed to be related to study intervention as assessed by investigators	0- No 1- Yes
Voluntary withdrawal	Qualitative/dichotomous	The volunteer decides to withdraw from study for any reason	0- No 1- Yes
Requirement of any medication with significant interactions	Qualitative/dichotomous	Requirement of any medication that has significant interactions with TDF/FTC during participation in study	0- No 1- Yes
Demographic variables			
Age	Quantitative/continuous	Age of volunteer at the beginning of the study	Number of years
Randomization date	Quantitative/continuous	Randomization date	Day/Month/Year
Date drug/placebo start	Quantitative/continuous	Date of drug/placebo start	Day/Month/Year
Sex	Cualitativa/nominal	Birth sex of patient	1- Feminine 2- Masculine
Site	Cualitativa/nominal	Research site where volunteer works	1-Hospital Universitario San Ignacio 2-Clínica Colombia 3-Clínica Reina Sofia

			4-Clinica Santa María del Lago 5-Hospital Universitario Nacional 6-Clinica Samaritana-Bogotá 7-Clinica Samaritana-Zipaquira 8-Hospital San Jorge
Profession	Qualitative/nominal	Profession	1- Physician 2- Nurse 3- Nursing assistant 4- Respiratory therapist
Department	Qualitative/nominal	Hospital department in which volunteer works. Multiple answers possible	1- Emergency department 2- Hospitalization floors 3- ICU
Time of daily exposure to COVID-19 patients	Quantitative/continuous	Declared average time of daily exposure per volunteer to COVID-19 patients	Number of hours
Shift	Qualitative/nominal	Volunteer's work shifts	1- Morning 2- Afternoon 3- Night 4- Whole day 5- Whole day and night shifts
Number of institutions in which volunteer works	Quantitative/ discrete	Number of institutions in which volunteer works	Number of institutions
Physician role in institution	Qualitative/nominal	Role of physician in the institution	1. Intern 2. General practitioner 3. Resident 4. Specialist 5. Not applicable
Specialty	Qualitative/nominal	Physician's specialty (or residency)	1. Emergency medicine 2. Internal medicine 3. Adult intensive care 4. Pediatric intensive care 5. Geriatrics 6. Anesthesiology 7. Pediatrics 8. Neonatology 9. Surgery 10. Surgical specialties 11. Pulmonology 12. Infectious diseases 13. Other 14. Not applicable
Weight	Quantitative/continuous	Weight at enrollment measured with a calibrated clinical scale	Weight in kilograms with one decimal
Height	Quantitative/continuous	Height at enrollment measured with a clinical stadiometer	Height in centimeters without decimals
Number of cohabitating people	Quantitative/discrete	Number of people that cohabit with volunteer	Number of people
Comorbidities			
Chronic obstructive pulmonary disease (COPD)	Qualitative/dichotomous	History of confirmed COPD as disclosed by the patient	0- No 1- Yes
Cardiovascular disease	Qualitative/nominal	History of hypertension, stroke, peripheral artery disease, heart failure	1- No 2- HTA 3- Stroke 4- PAD 5- HF
Diabetes mellitus	Qualitative/nominal	Classification of diabetes mellitus	0- No 1-Diabetes tipo I 2-Diabetes tipo II

Diabetes control	Qualitative/nominal	Controlled diabetes: defined as glycated A1C hemoglobin (HbA1C) equal or less than 7% within the last 3 months. Uncontrolled diabetes: defined as HbA1C higher than 7%.	1-Uncontrolled diabetes 2-Controlled diabetes 3-No HbA1C data
Data to be collected in Follow-up 1, Follow-up 2 y Follow-up 3			
Follow-up date	Quantitative/continuous	Date	Day/Month/Year
COVID-19 related symptoms	Qualitative/dichotomous	Development of any of the following symptoms: - Fever: body temperature higher than 38°C - Acute cough (start within the last 10 days) - Shortness of breath - Rhinorrhea - Sore throat - Malaise - Acute diarrhea - Anosmia or hyposmia - Dysgeusia - Headache	0- No symptoms 1- Fever 2- Acute cough 3- Shortness of breath 4- Rhinorrhea 5- Sore throat 6- Malaise 7- Acute diarrhea 8- Anosmia or hyposmia 9- Dysgeusia 10- Headache 11- Other, Specify
Date of symptom start	Quantitative/continuous	Date of start of first COVID-19 related symptom. If no symptoms register 00/00/00.	Day/Month/Year
Adverse event (AE)	Quantitative/nominal	Any untoward adverse event during administration of investigational product that may or may not have a causal relationship with it.	0-No 1-Yes
Serious adverse event (SAE)	Qualitative/nominal	Any adverse event that: - Results in death. - Threatens life and requires hospitalization or prolongation of hospitalization. - Results in permanent or prolonged inability or disability. - Causes congenital defects or malformations.	0-No 1-Yes
Serious adverse event classification	Qualitative/nominal	Expected SAE: An AE whose nature and severity is consistent with what is described in investigator's brochure or drug insert. Unexpected SAE: An AE whose nature and severity are not consistent with what is described in investigator's brochure or drug insert.	1- Expected serious adverse event 2- Unexpected serious adverse event
Fatal SAE	Qualitative/nominal	SAE that results in death	0- No 1- Yes
Type of SAE	Qualitative/nominal	Type of SAE the volunteer developed	1- Acute kidney injury 2- Proximal tubulopathy 3- Emesis 4- Abdominal pain 5- Headache 6- Insomnia 7- Diarrhea 8- Hypersensitivity skin reaction 9- Steven-Johnson's syndrome 10- Maculopapular rash 11- Appendicitis 12- Pancreatitis 13- Other, specify
Date of SAE start	Quantitative/continuous	Date when SAE started	Day/Month/Year
Date of SAE end	Quantitative/continuous	Date when SAE ended	Day/Month/Year

Non serious AE	Qualitative/nominal	Whether volunteer developed non serious AE	0- No 1- Yes
Type of non-serious AR	Qualitative/nominal	Type of non serious AE that volunteer developed	1- Nausea 2- Headache 3- Abdominal pain 4- Flatulence 5- Weakness or tiredness 6- Insomnia 7- Fatigue 8- Vomiting 9- Maculopapular rash 10- Steven-Johnson's syndrome 11- Allergic skin reaction 12- Other, specify
Nausea	Qualitative/nominal	A feeling of sickness featured by an urge to vomit.	1-Grade 1 2-Grade 2 3-Grade 3
Headache	Qualitative/nominal	Headache	1-Grade 1 2-Grade 2 3-Grade 3
Abdominal pain	Qualitative/Nominal	A feeling of distress or pain in abdominal area.	1-Grade 1 2-Grade 2 3-Grade 3
Flatulence	Qualitative/nominal	A disorder highlighted by abnormally increased gas discharge by lower gastrointestinal tract.	1-Grade 1 2-Grade 2
Insomnia	Qualitative/nominal	A disorder characterized by difficulty to start or maintain sleep.	1-Grade 1 2-Grade 2 3-Grade 3
Vomit	Qualitative/nominal	A disorder featured by a reflex act or actively regurgitating stomach contents through mouth	1-Grade 1 2-Grade 2 3-Grade 3 4-Grade 4 5-Grade 5
Maculopapular skin rash	Qualitative/nominal	A disorder featured by the appearance of macules and papules. Also known as morbilliform eruption. Often associated with pruritus.	1-Grade 1 2-Grade 2 3-Grade 3
Steven-Johnson's syndrome	Qualitative/nominal	A disease in which at least 10% of body surface area develops a severe sphenelating lesions and bullae, also compromising mucosal membranes.	3-Grade 3 4-Grade 4 5-Grade 5
Allergic reaction	Qualitative/nominal	A disorder featured by a local or diffuse skin reaction upon exposure to an allergenic.	1-Grade 1 2-Grade 2 3-Grade 3 4-Grade 4 5-Grade 5
Other allergic reaction	Qualitative/nominal	Se coloca la clasificación de la reacción alérgica reportada según la	1-Grade 1 2-Grade 2 3-Grade 3 4-Grade 4 5-Grade 5
Adherence by tablet count	Qualitative/discrete	Number of drug/placebo tablets taken to follow-up date	Number of tablets
Drug/placebo interruption	Qualitative/dichotomous	Any interruption of investigational product	0- No 1- Yes
Days of product interruption	Quantitative/discrete	Days of drug interruption	Number of days
Cause of drug interruption	Qualitative/nominal	Reason of drug interruption	1- Omission 2- AE 3- Accidental los of drug/placebo 4- Non-availability of drug/placebo
Additional data to be collected in Follow-up 2 and 3			

Temperature	Quantitative/continuous	Body temperature in Celsius degrees	Temperature in Celsius degrees
Heart rate	Quantitative/discrete	Heart rate	Heart rate in beats per minute
Respiratory rate	Quantitative/discrete	Respiratory rate	Respiratory rate in respirations per minute
Systolic blood pressure	Quantitative/discrete	Systolic blood pressure	Systolic blood pressure in mmHg
Diastolic blood pressure	Quantitative/discrete	Diastolic blood pressure	Diastolic blood pressure in mmHg
Creatinine	Quantitative/continuous	Serum creatinine concentration (mg/dl).	Serum creatinine concentration (mg/dl).
Creatinine rise	Qualitative/nominal	Severity of creatinine rise	0-Normal 1-Grado 1 2-Grado 2 3-Grado 3 4-Grado 4
IgG for SARS-CoV-2	Qualitative/dichotomous	Result of serology test for SARS-CoV-2 (only for follow-up 2)	0- Negative 1- Positive
Data to be collected in follow-up 3			
Platelets	Quantitative/discrete	Number of platelets in complete blood count (CBC)	Number of platelets per microliter (Cels/ μ l).
Thrombocytopenia	Qualitative/nominal	Severity of thrombocytopenia	0-Normal 1-Grade 1 2-Grade 2 3-Grade 3 4-Grade 4
Hemoglobin (Hb)	Qualitative/continuous	Hemoglobin concentration in CBC	Hb (g/dl).
Anemia	Qualitative/nominal	Classification of severity of anemia	0-Normal 1-Grade 1 2-Grade 2 3-Grade 3 4-Grade 4
Lymphocytes	Quantitative/discrete	Number of lymphocytes in complete blood count (CBC)	Number of lymphocytes per microliter (Cels/ μ l).
Lymphopenia	Qualitative/nominal	Classification of severity of lymphopenia	0-Normal 1-Grade 1 2-Grade 2 3-Grade 3 4-Grade 4
Neutrophils	Quantitative/discrete	Number of neutrophils in complete blood count (CBC)	Number of neutrophils per microliter (Cels/ μ l).
Neutropenia	Qualitative/nominal	Classification of severity of neutropenia	0-Normal 1-Grade 1 2-Grade 2 3-Grade 3 4-Grade 4
Aspartate aminotransferase (AST)	Quantitative/continuous	AST concentration in international units per liter (UI/l)	AST (UI/l).
Aspartate aminotransferase elevation	Qualitative/nominal	Severity of elevation of AST	0-Normal 1-Grade 1 2-Grade 2 3-Grade 3 4-Grade 4
Alanine aminotransferase (ALT)	Quantitative/continuous	ALT concentration in international units per liter (UI/l)	ALT (UI/l).
Alanine aminotransferase elevation	Qualitative/nominal	Severity of elevation of ALT	0-Normal 1-Grade 1 2-Grade 2 3-Grade 3 4-Grade 4

Pregnancy test	Qualitative/dichotomous	Applicable only to women. Result of quantitative serum Beta-HCG test regarding upper reference value for non-pregnant women.	0- Negative 1- Positive
RT-PCR SARS-CoV-2	Qualitative/dichotomous	Detection of SARS-CoV-2 by RT-PCR de	0- Undetectable 1- Detectable
Data to be collected only in Follow-up 4			
Follow-up date	Quantitative/continuous	Follow-up date	Day/month/year
COVID-19 related symptoms	Qualitative/dichotomous	Development of any of the following symptoms: - Fever: body temperature higher than 38°C - Acute cough (start within the last 10 days) - Shortness of breath - Rhinorrhea - Sore throat - Malaise - Acute diarrhea - Anosmia or hyposmia - Dysgeusia - Headache	0- No symptoms 1- Fever 2- Acute cough 3- Shortness of breath 4- Rhinorrhea 5- Sore throat 6- Malaise 7- Acute diarrhea 8- Anosmia or hyposmia 9- Dysgeusia 10- Headache 11- Other, Specify
Date of symptom start	Quantitative/continuous	Date of start of first COVID-19 related symptom. If no symptoms register 00/00/00.	Day/Month/Year
Temperature	Quantitative/continuous	Body temperature in Celsius degrees	Temperature in Celsius degrees
Heart rate	Quantitative/discrete	Heart rate	Heart rate in beats per minute
Respiratory rate	Quantitative/discrete	Respiratory rate	Respiratory rate in respirations per minute
Systolic blood pressure	Quantitative/discrete	Systolic blood pressure	Systolic blood pressure in mmHg
Diastolic blood pressure	Quantitative/discrete	Diastolic blood pressure	Diastolic blood pressure in mmHg
Serology IgG for SARS-CoV-2	Qualitative/dichotomous	Result of serology IgG test for COVID-19 before randomization and administration of drug/placebo	0- Negative 1- Positive
Dependent variables/primary outcomes			
Development of COVID-19	Qualitative/dichotomous	Positive RT-PCR for SARS-Cov-2 at any time during follow-up	0- No 1- Si
Date of positive RT-PCR for SARS-CoV-2	Quantitative/continuous	Date of positive result	Day/Month/Year
Time to positive result positive RT-PCR for SARS-CoV-2	Quantitative/discrete	Time between start of administration of drug/placebo to a positive RT-PCR result.	Number in days
Symptoms probably related to COVID-19	Qualitative/nominal	Recording of presence or absence of solicited symptoms probably related to COVID-19 during each of 4 follow-up visits.	0-None 1-Fever 2-Acute cough 3-Shortness of breath 4-Rinorrhea 5-Sore throat 6-Malaise 7-Acute diarrhea 8-Anosmia hyposmia 9-Dysgeusia 10-Mialgya 11-Other, specify
Date of symptom start	Quantitative/continuous	Date of start of first COVID-19 related symptom. If no symptoms register 00/00/00.	Day/Month/Year
Time to development of first COVID-19 related symptom	Quantitative/discrete	Number of days between start of administration of drug/placebo and appearance of first COVID-19 related symptom	Number of days
Dependent variables/secondary outcomes			

Withdrawal of investigational product	Qualitative/nominal	Decision by investigator or patient to withdraw investigational product before planned.	0-Not applicable 1- Withdrawal due to kidney dysfunction. 2- Withdrawal due to need for new interacting medications. 3- Withdrawal due to development of any SAE deemed to be related to intervention. 4- Withdrawal due to any AE that makes the volunteer decide to interrupt investigational product. 5-Voluntary withdrawal.
Date of investigational product withdrawal	Quantitative/continuous	Date of discontinuation of investigational product, only if previous answer was other than 0	Day/month/year
Time to discontinuation of investigational product	Quantitative/discrete	Time between initiation of investigation product to discontinuation	Number of days
Severity of COVID-19	Qualitative/nominal	Classification of severity as follows: - Asymptomatic infection - Mild disease: defined as not requiring hospitalization. - Moderate disease: defined as requiring hospitalization outside of the ICU. - Severe disease: defined as requiring hospitalization in ICU.	1-Asymptomatic 2-Mild 3-Moderate 4-Severe
Date of hospitalization start	Quantitative/continuous	Date of hospitalization start	Day/month/year
Date of hospital discharge	Quantitative/continuous	Date of hospital discharge	Day/month/year
Date of ICU admission	Quantitative/continuous	Date of ICU admission	Day/month/year
Fecha de egreso del UCI	Quantitative/continuous	Date of ICU discharge or date of death	Day/month/year
Date of recovery from COVID-19	Quantitative/continuous	Recovery from COVID-19 defined as a minimum of 10 days after symptom start plus at least 72 hours of symptom improvement. If the patient died, record 00/00/00	Day/month/year
Final status	Quantitative/continuous	Record of volunteer status at the end of follow-up	0- Death 1- Alive
Date of end of follow-up	Quantitative/continuous	Date of end of follow-up	Day/month/year

References

1. Daihai H, Daozhou G, Zhuang Z, Peihua C, Yijun L, Lin Y. The attack rate of the COVID-19 in a year. :3–5.

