3.1. Study design

Randomized triple-blinded multicentric clinical trial, conducted in parallel, with two arms:

The trial will be performed with health care workers (Physicians, Nurses, Respiratory therapists, or nurse assistants) free of SARS-CoV-2 infection prior, recent or at the time of the inclusion and who directly care for confirmed or suspected cases of COVID-19 in the emergency room, general COVID wards or intensive care units. A screening at baseline will be carried out in order to evaluate for eligibility by performing: SARS-CoV-2 RT-PCR, SARS-CoV-2 IgG antibodies, as well as, hemogram, creatinine, serum phosphorus, AST, ALT, ELISA for HIV, surface Hepatitis B antigen antibodies, qualitative pregnancy test (b-HCG). Once

eligibility is verified participants will be randomly assigned to either an intervention or a control group.

The interventions consists in the administration of Tenofovir/ Emtricitabine (300 mg / 200 mg daily during 60 days) + Personal Protective Equipment (PPE) and the control consists in the administration of placebo (1 tablet daily during 60 days) + Personal Protective Equipment (PPE)

All participants will have PPE recommended for the preventions of COVID-19 by the WHO which include mayo dress, nonfluid long sleeve gown, ocular protection with goggles, face shield or visor and surgical mask in procedures that do not aerosolize. N-95 respirators are required for procedure that generate aerosols. For detailed description see Table 2.

The re-use of N-95 respirators will be allowed according to CDC and WHO guidelines. This taking into consideration the shortage of supplies for the actual situation. The N-95 continuous use will be for 8 hours and the N-95 intermittent use will be allowed up to 5 times with the precaution of storage in a paper and plastic bag label them with the participant name and placed them in a plastic recipient at the end of shifts(48).

After baseline evaluation and confirming eligibility an initial visit and 4 follow up visits at day 20, 40, 60, 75 days will be carried out. See Table 1 and Graph 1.

In the case of presenting COVID-19 related symptoms at any time after enrolling a SARS-CoV2 RT-PCR will be performed between day 1 to 5 of the onset of symptoms and will be repeated it after 72 hours in case that the first one is negative. In the case of having any positive SARS-CoV2 RT-PCR or SARS-CoV2 IgG SARS-CoV2 infection will be confirmed and the intervention will be suspended.

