will be confirmed. While confirmation RT-PCR arrives, the participant will not quit taking the intervention. In that scenario, the intervention will only be suspended in the case of a highly suspected case or severe case requiring hospitalization.

In case the infection is ruled out in the follow up, the participant will continue the interventions and follow up scheduled, according to graph 1.

With regards to diagnostic testing during follow up as shown in table 1. IgG antibodies will be done at visit 2 and 4 (40 days from initially taking the intervention and 15 day after finalizing it). This considering volunteer that might acquire the infection in the last days of the pharmacological intervention. Moreover, at day 60, last of the intervention, an RT-PCR will be performed to all participants. This in order to detect participants who develop asymptomatic infection. The research group is aware that this follow up will not identify a 100% of the asymptomatic infection for the low sensitivity of testing in this scenario, approximately 30 to 40% (46,47), yet it will be done in both arms.

Importantly, for the covid-19 emergency, clinical follow up, adverse event reporting and adherence reporting could be done online.

Personal Protective Equipment

All volunteers will be using the following personal protective equipment. This based on the guidelines of the WHO (23). See table 2.

Table 2. Use of PPE by study volunteers.

Area	Health care personnel or patients	Activity	Type of PPE or activity
Emergency room, general COVID wards or intensive care units	Health care workers	Direct contact with the patient of non-aerosol generating procedures.	Surgical mask Visor or glasses. Long sleeve gown Nonsterile gloves.
		Direct contact with the patient and aerosol generating procedures.	N95 respirator Visor or glasses. Long sleeve gown Nonsterile gloves. May dress

			under the robe that is removed at the end of the shift
Other areas of transit (hallways or waiting rooms)	All personnel including health care workers	Any activity that does not involve contact shorter than 2 meters in distance between people	Surgical mask

Adapted from: Rational use of personal protective equipment for coronavirus disease 2019 (COVID-19). Interim guidance 27 February 2020. World Health Organization. (23)

*Health care worker: person in whose activity directly care a contact, suspected, or confirmed case of COVID-19.

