3.6.9. Procedure in case of presenting the primary outcome

If the volunteer, after the start of the study, has a positive result of RT-PCR or IgG for SARS CoV2, which confirms the infection by COVID 19, they will be contacted virtually or in person. During this intervention, the following actions will be carried out:

- You will be given information about your result, and you will be instructed to contact your occupational risk and health insurer.
- The presence of alarm signs (drowsiness, dyspnea, cyanosis) will be evaluated. In case of any of these symptoms are present, the patient will be instructed to attend the emergency service, to receive treatment in accordance with current national and institutional guidelines.
- The volunteer will be instructed to suspend the intervention product, and the masking will be released.
- National Public Health Surveillance System mandatory notification form will be filled out, the institution where the volunteer works will be informed, and the completed form will be sent.

- The volunteer will be informed that telephone follow-up will be carried out every 5 days until the symptoms are resolved or a maximum of six weeks after the diagnosis of COVID 19. In case of presenting any alarm sign during the follow-up, the patient will be recommended to attend the emergency department.

During the telephone follow-up, the volunteer's primary outcome (COVID 19 infection) will be classified as follows: asymptomatic, mild, moderate, or severe COVID. If the patient does not answer due to physical impossibility (e.g. intubation), communication with a companion or family member previously authorized by the patient will be sought.

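### Follow-up forms count cough only if it began in the last 10 days although visits are 15 to 20 days apart, and code 10 means headache on the forms but myalgia in the outcome variable

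*Combined protocol and SAP*

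**What the plan says.** Section 3.1 sets the schedule: "4 follow up visits at day 20, 40, 60, 75 days will be carried out". Section 3.6 adds the serology timing: "IgG antibodies will be done at visit 2 and 4", that is, days 40 and 75.

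In Appendix 3, the form for follow-ups 1 to 3 and the form for follow-up 4 carry the same cough item, "Acute cough (start within the last 10 days". No other symptom on either form has a time limit. Both forms end their code list with "9- Dysgeusia 10- Headache 11- Other, Specify" and ask for the start date of the first COVID-19 symptom.

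The same appendix then defines an outcome symptom variable, described as "Recording of presence or absence of solicited symptoms probably related to COVID-19 during each of 4 follow-up visits". Its list ends with "9-Dysgeusia 10-Mialgya 11-Other, specify". A further variable counts the days from first dose to first symptom.

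Severity is assigned separately. Under the procedure for participants who reach the primary outcome (section 3.6.9): "During the telephone follow-up, the volunteer's primary outcome (COVID 19 infection) will be classified as follows: asymptomatic, mild, moderate, or severe COVID". Those calls begin after a positive RT-PCR or IgG.

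**The concern.** A 10-day limit on cough suits screening and a prompt symptom report. The eligibility criteria and the trigger for symptomatic testing in section 3.6 use it that way. At a scheduled visit it is shorter than every interval the visit has to cover. The code lists then disagree on what code 10 means, although the outcome variable is recorded at the same visits.

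The affected symptoms are common. Section 1.3 cites headache in 70.3%, cough in 63.2% and myalgia in 62.5% of mild-to-moderate cases. Headache is also among the most common drug effects listed in section 5.1.1.

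Comparing clinical course and severity between arms is a specific objective (section 2.2). At stake are the symptom profile, the date of first symptom and, for infections found only by IgG, the line between asymptomatic and mild.

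**Working it through.** The plan states no figure on this point, so there is none to reproduce. The check is arithmetic on the schedule and a comparison of the lists.

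**Cough window.** Inputs: start at day 0 and visits at days 20, 40, 60 and 75 (section 3.1, Table 1); a 10-day window (Appendix 3).

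- Gaps: 20 − 0 = 20; 40 − 20 = 20; 60 − 40 = 20; 75 − 60 = 15.
- Uncovered days = gap − 10: 10, 10, 10 and 5, in total 35.
- Whole follow-up: 35/75 = 46.7%.
- Before the day-40 IgG: (10 + 10)/40 = 50%.
- From the day-40 to the day-75 IgG: (10 + 5)/35 = 42.9%.

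If whole days are counted and both ends of each window are eligible, the missed days are 1–9, 21–29, 41–49 and 61–64. That is 9 + 9 + 9 + 4 = 31 of 75 (41.3%), which leads to the same conclusion. Either figure is a share of follow-up time. It equals the share of cough onsets only if onsets are spread evenly.

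**Effect on the onset date.** Take a hypothetical participant, first dose on day 0, with cough from day 24 and loss of smell from day 28, seen at day 40. The cough began 16 days earlier and falls outside the window. If the site therefore does not count it, the first-symptom date becomes day 28 and the time to first symptom is 4 days too long.

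**Code lists.**

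| | Visit forms (follow-ups 1–4) | Outcome symptom variable |
|---|---|---|
| Code 10 | Headache | Myalgia |
| Headache listed | Yes | No |
| Myalgia listed | No | Yes |
| Code 11 | Other | Other |

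If codes are carried over, headache becomes myalgia. If labels are matched, headache can only go under the free-text code, and myalgia has no solicited source.

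**Route to an asymptomatic label.** Through the cough window, this needs an IgG-only case whose only symptom is cough, with onset in an uncovered period, not reported elsewhere and not brought out on the call. The documents do not give these shares. As an illustration, take the planned risks in section 3.4: 475 × 0.10 + 475 × 0.05 = 71.25 infections. Assume that 20–60% are found only by serology, that 2–10% of those have cough alone, and that onsets are even:

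- Low: 71.25 × 0.20 × 0.02 × 35/75 = 0.13 cases.
- High: 71.25 × 0.60 × 0.10 × 35/75 = 2.0 cases.

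This is before any rescue by other records. It covers the cough route only. It does not count cases with other resolved symptoms that the caller does not ask about.

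**The case against.** The best defence is that little follows from either slip. The 10 days may be meant only to define an acute cough. The limit touches cough alone, and the start-date field has no limit. There are other routes of capture: prompt reporting by app or phone (section 3.6), the diary (section 3.6.5), adverse-event records whose definition includes symptoms (sections 6.1 and 6.2), and a physician's evaluation at each visit. No section derives severity from the visit codes. The analysis of severity is descriptive (section 4), and both arms use the same forms.

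Most of this stands and limits the size of the point. It does not remove it. Symptomatic testing under section 3.6 needs two symptoms from a list that omits headache, rhinorrhea and myalgia, so cough with headache counts as one. The diary is described for adverse events, exposure hours and PPE use, without a COVID-19 symptom list. No section says that diary or adverse-event entries feed the severity class. The equal-arms argument is weaker for the telephone calls, because section 3.6.9 releases the masking at diagnosis.

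A reader might infer two stronger things. The first is that the code conflict turns mild cases into asymptomatic ones. It cannot: headache and myalgia are both non-zero codes, and a free-text code exists. The second is that most IgG-detected cases would be called asymptomatic, because the mean symptom duration cited in section 1.3 (11.5 ± 5.7 days) is short against the IgG schedule. That reasoning shows how many may be symptom-free when called. It shows misclassification only if callers record current symptoms alone, which section 3.6.9 does not say.

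**Conclusion.** Both defects are in the text, and both are minor. Read literally, the cough item leaves 35 of 75 days (46.7%) outside every window, and code 10 has two meanings. Cough data can be lost, the date of and time to first symptom can be wrong, and headache can be read as myalgia if codes are carried over.

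A few IgG-only cases whose symptoms had resolved may be classed as asymptomatic, because the telephone classification gives no look-back. Section 3.3 makes mild infection symptomatic, so past symptoms decide that class. The number cannot be derived from the documents and is probably small; the range of 0.13 to 2.0 for the cough route rests on assumed shares.

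Appendix 3 files the symptom variables under its primary-outcome heading, but section 3.3 defines the primary outcome by RT-PCR or IgG alone. The effect is therefore limited to descriptive secondary data. The sample size and the primary analysis are untouched.

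**What to change.** 1. On all follow-up forms, ask about each symptom since the last visit, cough included.
2. Use one symptom list and one code set for the visit forms and the outcome variable, with headache and myalgia as separate codes.
3. In section 3.6.9 and the severity entry of Appendix 3, state that severity in IgG-only cases is the worst status since the last negative test.

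The first change brings the uncovered time from 35 days to 0, and the second removes the code conflict. A fixed look-back before a positive RT-PCR is not proposed, since the documents give no basis for one.

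The cost is form wording, a code table and one sentence. Recall over 15 to 20 days is somewhat less precise than over 10.
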